13.4 Demographic and Baseline Characteristics

By-population tabulation summaries and by-subject listings of demographics, baseline characteristics, disease history, and historical transfusion burden will be presented in the Safety Analysis Set.

The demographic and baseline characteristics consist of:

- Age (years) –as numeric value
- Sex (Female, Male)
- Ethnicity (Categories as collected from CRF)
- Race (Categories as collected from CRF)
- Height (cm)
- Weight (kg)
- BMI (kg/m^2)
- Baseline Eastern Cooperative Oncology Group (ECOG) Score (0, 1)
- Region (Europe/North America, Asia/Africa) (see Appendix 5 for countries included in each region)
- Beta Thalassemia Diagnosis (Major, Intermediate, E)
- Concomitant Alpha Gene Status (Deletion, Duplication/Triplication, No Alpha)

- Previous/Ongoing Cardiac and/or Hepatic Co-morbidities due to Iron Overload (TDT) (Yes, No)
- Baseline Transfusion Burden in Packed RBC Units (day -83 to 1) continuously and categorically categorized level: Low Transfusion Burden (≤ 5), Medium Transfusion Burden ($> 5 < 7$) and High Transfusion Burden (> 7) [TDT]
- Pre-transfusion Hemoglobin Threshold, defined as mean of all documented pre-transfusion hemoglobin values during the 12 weeks prior to Dose 1 Day 1 (continuous and categorized level: < 9 g/dL and ≥ 9 g/dL) [TDT]
- Baseline Serum Ferritin –as numeric value
- Daily Iron Chelation Use (Yes, No)
- Splenectomy (Yes, No)
- Baseline Hemoglobin (≤ 8.5 , > 8.5) [NTDT]

13.4.1 Medical and Surgical History

Medical and surgical history will be coded using Medical Dictionary for Regulatory Activities (MedDRA) Version 23.0 or higher and will be summarized for each population by treatment arm and total in the Safety Analysis Set, using System Organ Class (SOC) and MedDRA preferred term (PT). The table will include the number and percentage of subjects and will be sorted alphabetically by SOC and in decreasing frequency by PT and then alphabetically for ties (based on the total count in the analysis set). A subject will only be counted once within a class.

A by-subject listing for medical and surgical history generated on the Safety Analysis Set.

13.5 Prior and Concomitant Treatments and Procedures

13.5.1 Prior and Concomitant Beta-Thalassemia Treatment

A prior Beta-Thalassemia treatment is any medication taken prior to first dose of study drug that is reported on the Prior/Concomitant Medications eCRF and categorized as “Disease Under Study” under the “Primary Reason Medication was Taken/Therapy was Given”. A concomitant Beta-Thalassemia treatment is any medication ongoing at the time of the first dose of study drug, or that started after first dose and within 30 days of the last dose of study drug, that is reported on the Prior/Concomitant Medications eCRF and categorized as “Disease Under Study” under the “Primary Reason Medication was Taken/Therapy was Given”.

The number and percentage of subjects taking prior Beta-Thalassemia treatment will be tabulated for each population by treatment arm, the combined active arms, and the total using the World Health Organization Drug Dictionary (WHO-DD) (01MAR2020 or later) standardized medication name for the Safety Analysis Set. Medications will be classified by Anatomical Therapeutic Chemical (ATC) level 2 groups, then by preferred name within each ATC group. If the ATC level 2 group is missing, the next non-missing level will be used. Subjects will only be counted once within each ATC group and each preferred name. ATC groups will be sorted alphabetically and preferred name will be sorted in descending frequency, using the numbers in the combined active arms column, and then alphabetically in the event of any ties.

The number and percentage of subjects taking concomitant Beta-Thalassemia treatment will be tabulated for each population by treatment arm and the combined active arms using the World Health Organization Drug Dictionary (WHO-DD) (01MAR2020 or later) standardized medication name for the Safety Analysis Set. Medications will be classified by Anatomical Therapeutic Chemical (ATC) level 2 groups, then by preferred name within each ATC group. If the ATC level 2 group is missing, the next non-missing level will be used. Subjects will only be counted once within each ATC group and each preferred name. ATC groups will be sorted alphabetically and preferred name will be sorted in descending frequency, using the numbers in the combined active arms column, and then alphabetically in the event of any ties.

All prior and concomitant Beta-Thalassemia treatment data will be presented in a listing based on the Safety Analysis Set for TDT and NTDT subjects.

13.5.2 Prior and Concomitant Medications

Prior medications are medications that started before the first dose of study drug. Concomitant medications are medications ongoing at the time of the first dose of study drug, or that started after first dose and within 30 days of the last dose of study drug.

The number and percentage of subjects who took prior medications will be tabulated for each population by treatment arm, the combined active arms, and the total using the WHO-DD (01MAR2020 or later) standardized medication name for the Safety Analysis Set. Medications will be classified by ATC level 2 groups, then by preferred name within each ATC group. If the ATC level 2 group is missing, the next non-missing level will be used. Subjects will only be counted once within each ATC group and each preferred name. ATC groups will be sorted alphabetically and preferred name will be sorted in descending frequency, using the numbers in the combined active arms column, and then alphabetically in the event of any ties.

The number and percentage of subjects taking concomitant medications will be tabulated for each population by treatment arm and the combined active arms using the WHO-DD (01MAR2020 or later) standardized medication name for the Safety Analysis Set. Medications will be classified by ATC level 2 groups, then by preferred name within each ATC group. If the ATC level 2 group is missing, the next non-missing level will be used. Subjects will only be counted once within each ATC group and each preferred name. ATC groups will be sorted alphabetically and preferred name will be sorted in descending frequency, using the numbers in the combined active arms column, and then alphabetically in the event of any ties.

All prior and concomitant medications data will be presented in a listing based on the Safety Analysis Set for TDT and NTDT subjects.

13.5.3 Concomitant Procedures

Concomitant procedures are procedures ongoing at the time of the first dose of study drug, or that started after first dose and within 30 days of the last dose of study drug. The number and percentage of subjects having concomitant procedures will be tabulated for each population by treatment arm and the combined active arms using MedDRA (version 23.0 or later) for the Safety Analysis Set. Procedures will be classified by SOC, then by PT. Subjects will only be counted once within each SOC and PT. The SOCs and PTs will be sorted alphabetically by SOC and in decreasing frequency by PT using the numbers in the combined active arms column, and then alphabetically in the event of any ties (based on the total count in the analysis set).

All concomitant procedures data will be presented in a listing based on the Safety Analysis Set for TDT and NTDT subjects. In addition, a listing of concomitant procedures that are reported on the Concomitant Procedures eCRF and categorized as "Disease Under Study" under the "Primary Reason Procedure was Performed", based on the Safety Analysis Set for TDT and NTDT subjects, will be provided.

13.5.4 Prior and Concomitant Iron Chelation Therapy

Prior iron chelation therapies are defined as therapies that were started before the first dose of study drug that are reported on the Iron Chelation Therapy eCRF. Concomitant iron chelation therapies are therapies ongoing at the time of the first dose of study drug, or that started after first dose and within 30 days of the last dose of study drug, that are reported on the Iron Chelation Therapy eCRF.

The number and percentage of subjects who took prior iron chelation therapies will be tabulated for each population by treatment arm, the combined active arms, and the total using the WHO-DD (01MAR2020 or later) standardized medication name for the Safety Analysis Set. Medications will be classified by ATC level 2 groups, then by preferred name within each ATC group. If the ATC level 2 group is missing, the next non-missing level will be used. Subjects will only be counted once within each ATC group and each

preferred name. ATC groups will be sorted alphabetically and preferred name will be sorted in descending frequency, using the numbers in the combined active arms column, and then alphabetically in the event of any ties.

The number and percentage of subjects taking concomitant iron chelation therapies will be tabulated for each population by treatment arm and the combined active arms using the World Health Organization WHO-DD (01MAR2020 or later) standardized medication name for the Safety Analysis Set. Medications will be classified by Anatomical Therapeutic Chemical (ATC) level 2 groups, then by preferred name within each ATC group. If the ATC level 2 group is missing, the next non-missing level will be used. Subjects will only be counted once within each ATC group and each preferred name. ATC groups will be sorted alphabetically and preferred name will be sorted in descending frequency, using the numbers in the combined active arms column, and then alphabetically in the event of any ties. All prior and concomitant iron chelation therapies data will be presented in a listing based on the Safety Analysis Set for TDT and NTDT subjects.

13.6 Endpoint Analyses

Endpoint analyses for TDT and NTDT populations will be reported separately. All efficacy endpoints will be conducted using the PP Analysis Set and may be repeated for the mITT Analysis Set (if applicable), and the ITT Analysis Set (where applicable).

13.6.1 Hypothesis Testing Strategy and Multiplicity

There will be no adjustment for multiple testing.

13.6.2 Safety Analyses

The below information regarding safety analyses is relevant for both the TDT and NTDT populations. The two populations will be summarized separately.

IMR-687 safety and tolerability will be measured in both populations by:

- Incidence and severity of AEs and SAEs
- Incidence of subjects with a post-Baseline clinically significant worsening in the CTCAE laboratory grade for a lab parameter
- Incidence of subjects with a post-Baseline clinically significant change in a vital signs parameter
- Incidence of subjects meeting the clinically significant criteria for an electrocardiogram (ECG) parameter
- Changes from Baseline in clinical laboratory tests (hematology, coagulation chemistry, urinalysis), vital signs (continuous parameters only) for any timepoint and 12-lead ECG parameters
- Changes in physical examination findings relative to the Baseline physical examination

13.6.2.1 Adverse Events

MedDRA Coding

AEs will be coded using MedDRA (v23.0 or higher).

Treatment-emergent adverse event (TEAE)

A treatment-emergent adverse event (TEAE) is defined as an AE that emerges on or after the initiation of study drug, or an AE that existed pre-treatment and worsened in severity on or after the initiation of study drug, through 30 days after the last dose of study drug. A pre-treatment adverse event is an AE that emerges before the date of initiation of study drug.

Refer to Appendix 3 for handling of partial dates for AEs for the purpose of assigning treatment-emergent flags. In the case where it is not possible to define an AE as treatment emergent or not, the AE will be classified as treatment emergent.

Severity

Severity is classified as Grade 1: Mild, Grade 2: Moderate, Grade 3: Severe, Grade 4: Life Threatening, Grade 5: Death Related to AE, using the Common Terminology Criteria for Adverse Events, v5.0 (CTCAE v5.0). For the AE summary by CTCAE severity grade, an AE with missing CTCAE severity grade will not be imputed. Imputed values will not be included in data listings.

Relationship to Study Treatment

Relationship is classified as “Unlikely/Not related”, “Possible”, “Probably/Likely”, or “Certain/Related” by the Investigator. A “treatment-related TEAE” for the purpose of this summary is defined as a TEAE with relationship to study drug of “Possible”, “Probably/Likely” or “Certain/Related”. For the AE summary by relationship, an AE with a missing relationship to study drug will not be imputed. Imputed values will not be included in data listings.

TEAEs Leading to Discontinuation of Study Treatment

TEAEs leading to discontinuation of study treatment will be identified by action taken with study treatment being recorded as “Drug withdrawn” on the Adverse events CRF.

Serious and Non-Serious TEAEs

Serious adverse events (SAEs) are those events recorded as “Yes” for the question “Was the adverse event serious?” on the Adverse Event CRF.

TEAEs Leading to Death

TEAEs leading to death are those events which are recorded as “Yes” for the question “Did the adverse event result in death?”, or recorded CTCAE Toxicity Grade 5, or with outcome = “Fatal” on the Adverse Events CRF.

TEAEs Leading to Study Discontinuation

TEAEs leading to study discontinuation are those events which are recorded as “Yes” for the question “Did the adverse event cause the subject to be discontinued from the study?” on the Adverse events CRF.

TEAEs Leading to Dose Reduction

TEAEs leading to dose reduction will be identified by action taken with study treatment being recorded as “Dose Reduced” on the Adverse events CRF.

A summary of TEAEs will be presented by treatment arm and the combined IMR-687 treatment arms for TDT and NTD subjects. The number and percentage of subjects reporting any of the following categories will be provided:

- Any pre-treatment adverse event
- Any TEAE
- Grade 3 or higher TEAEs
- Treatment-related TEAEs
- Treatment-related grade 3 or higher TEAEs
- TEAEs with outcome of death
- SAEs
- Treatment-related SAEs

- Treatment-related grade 3 or higher SAEs
- Treatment-related grade 2 or higher TEAEs
- TEAEs leading to discontinuation of study drug
- Treatment-related TEAEs leading to discontinuation of study drug
- TEAEs leading to study discontinuation
- Treatment-related TEAEs leading to study discontinuation
- TEAEs leading to dose reduction
- Treatment-related TEAEs leading to dose reduction

The following AE tables will be summarized by treatment arm and the combined IMR-687 treatment arms, SOC and PT (according to the MedDRA dictionary version 23.0 or higher) for TDT and NTDT subjects. SOCs will be sorted alphabetically and PTs will be sorted by descending frequency, by the combined IMR-687 treatment arm column, and then alphabetically for ties.

- The number and percentage of subjects reporting each TEAE. The AE count will be by subject, not event, and subjects are only counted once within each SOC or PT
- The number and percentage of subjects reporting treatment-related TEAEs. Subjects with multiple events within a particular SOC or PT will be counted under the category of their most drug-related event within that SOC or PT. AEs will be considered related to study drug if they are reported as certain/related, probably/likely related, and possibly related.
- The number and percentage of subjects reporting TEAEs, by severity (Grade 1, Grade 2, Grade 3, Grade 4, Grade 5, all defined in Section 12.1.2.2.1 of the study protocol), will also be provided. Subjects with multiple events within a particular SOC or PT will be counted under the category of their most severe event within that SOC or PT. AE severity (intensity) will be graded using NCI CTCAE, version 5.0
- The number and percentage of subjects reporting treatment-related TEAEs, by severity
- The number and percentage of subjects reporting Grade 3 or higher TEAEs
- The number and percentage of subjects reporting treatment-related Grade 3 or higher TEAEs
- The number and percentage of subjects reporting treatment-related Grade 2 or higher TEAEs
- The number and percentage of subjects reporting AEs leading to discontinuation of study drug
- The number and percentage of subjects reporting treatment-related TEAEs, by relationship
- SAEs
- TEAEs leading to death

The following AE tables will be summarized by treatment arm and the combined IMR-687 treatment arms, and PT for TDT and NTDT subjects. PTs will be sorted by descending frequency, by the combined IMR-687 treatment arm column, and then alphabetically for ties.

- The number and percentage of subjects reporting each TEAE.
- The number and percentage of subjects reporting treatment-related TEAEs
- The number and percentage of subjects reporting each TEAE with frequency $\geq 10\%$
- The number and percentage of subjects reporting treatment-related TEAEs with frequency $\geq 10\%$

All AEs (including non-treatment-emergent events) recorded on the CRF, all SAEs, and all deaths that occur following the first dose of study drug will be listed. All AE tables and listings will be reported using the Safety Analysis Set.

13.6.2.2 Clinical Laboratory Evaluation

Clinical laboratory tests (serum chemistry, central laboratory hematology, local laboratory hematology, and specialty hematology) will be summarized using the Safety Analysis Set and will be evaluated and presented using International System of Units (SI) unless otherwise stated. Clinical laboratory values will be graded from Grade 1 to Grade 4 using the NCI CTCAE, version 5.0. Post-Baseline laboratory values will only be compared to Baseline values from the same source. For example, local laboratory post-Baseline results can only be compared to local laboratory Baseline results.

Hematology assessments include: RBC count (mean corpuscular volume [MCV], RDW, mean corpuscular Hb, and mean corpuscular Hb concentration), hematocrit, Hb, platelets, WBC count (with differential: basophils, eosinophils, neutrophils, monocytes, and lymphocytes), erythrocyte count, and reticulocyte count and reticulocyte percentage. Some of these assessments are also considered PD endpoints, further detailed in the exploratory endpoint section below.

Specialty hematology assessments include: HbF and F-cells (%).

Coagulation assessments include: PT, aPTT, and international normalized ratio (INR).

Serum chemistry assessments include: alanine aminotransferase (ALT), albumin, alkaline phosphatase (ALP), aspartate aminotransferase (AST), bicarbonate, blood urea nitrogen (BUN), chloride, calcium, creatinine, glucose, lactate dehydrogenase (LDH), sodium, potassium, magnesium, phosphate, bilirubin (total, direct, and indirect), creatine kinase, total protein, glomerular filtration rate (GFR), and gamma-glutamyl transferase (GGT). Follicle stimulating hormone (FSH) will be included as well, but this is only collected for post-menopausal women at screening. Some of these assessments are also considered PD endpoints, further detailed in the exploratory endpoint section below.

Descriptive statistics (N, mean, SD, median, Q1, Q3, minimum, and maximum) for the observed, change from Baseline, and percent change from Baseline values will be summarized by visit, treatment arm, and the combined IMR-687 treatment arms, and presented separately for chemistry and hematology and for each population. Study Baseline defined in Section 10.1.2 will be used for change from baseline. Note that character urinalysis tests will only be listed.

Urinalysis assessments include: appearance, color, pH, specific gravity, ketones, protein, glucose, bilirubin, and urobilinogen, including occult blood and microscopic examination of sediment (only if occult blood is detected).

Shift tables will be used to summarize the shift from Baseline grade to maximum CTCAE grade (Grade 1 to 4 and Missing) for selected hematology and chemistry parameters listed in Appendix 4, by treatment arm and the combined IMR-687 treatment arms and presented separately for each population. Any subject with a post-Baseline result meeting the criteria, including those collected at unscheduled visits, will be included in the tabulation.

Potentially clinically significant (PCS) Criteria for hepatic function and renal function are shown in Table 5 below. The number and percentage of subjects meeting these PCS criteria will be summarized for hepatic function parameters (ALT, AST, ALP, and total bilirubin), the renal function parameter (serum creatinine), and platelet count separately. Any subject with any post-baseline result (including "unscheduled" visits) meeting the criteria will be included in the tabulation.

Table 5 PCS Criteria for Hepatic Function, Renal Function, and Platelet Count

Hepatic Function	Renal Function	Platelet Count

 ○ Post-baseline Alanine Aminotransferase (ALT) $\geq 3 \times$ upper limit of normal (ULN) ○ Post-baseline Aspartate Aminotransferase (AST) $\geq 3 \times$ ULN ○ Post-baseline Direct Bilirubin (BILDIR) $\geq 2 \times$ ULN ○ Post-baseline ALT/AST and BILDIR (ALT $\geq 3 \times$ ULN or AST $\geq 3 \times$ ULN) and BILDIR $\geq 2 \times$ ULN (Hy's Law) 	
 ○ Post-baseline Creatinine Clearance (CREATCLR) $< 0.5 \times$ baseline ○ Post-baseline Serum Creatinine (CREAT) $> 2 \times$ baseline 	
 ○ Post-baseline Platelet Count $> 1000 \times 10^9/L$

The following figures will be provided for the following hematology, chemistry, and coagulation results: MCV, platelets, neutrophils, reticulocyte (absolute and percent), GGT, LDH, creatinine, AST, ALT, indirect bilirubin, ACR.

- Shift plot from baseline to post-baseline maximum value for each parameter by treatment arm and for the combined IMR-687 treatment arms;
- Box and whisker plot for each lab parameter by visit for each treatment arm and the combined IMR-687 treatment arms.

All laboratory parameters (serum chemistry, central laboratory hematology, local laboratory hematology, specialty hematology, coagulation, and urinalysis) will be displayed in individual subject data listings. In addition, a listing of only abnormal laboratory values will be provided. All lab tables and listings will be reported on the Safety Analysis Set.

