9.0 Study Endpoints, Variables and Covariates

Primary Endpoints	TDT	NTDT
IMR-687 safety and tolerability assessed using: 
• Incidence and severity of adverse events and serious adverse events• Incidence of subjects with a post-Baseline clinically significant worsening in the CTCAE laboratory grade for a lab parameter	X	X

 Incidence of subjects with a post-Baseline clinically significant change in a vital signs parameter Incidence of subjects meeting the clinically significant criteria for an electrocardiogram (ECG) parameter Changes from Baseline in 12-lead ECG clinical laboratory test (chemistry, hematology, coagulation, and urinalysis), and vital signs parameters (continuous parameters only) Changes in physical examination findings relative to the Baseline physical examination 		
Secondary Endpoints	TDT	NTDT
Proportion of subjects with a $\geq 20\%$ reduction in RBC transfusion burden with a reduction of at least 2 units of RBCs (hematological improvement) for Week 12 to Week 24 and Week 24 to Week 36, compared to the 12 weeks prior to Baseline (Day 1).	X	
Proportion of subjects with a $\geq 20\%$ reduction in RBC transfusion burden with a reduction of at least 2 units of RBCs (hematological improvement) for Week 12 to Week 36, compared to the 12 weeks prior to Baseline (Day 1).	X	
Proportion of subjects with a $\geq 20\%$ reduction in RBC transfusion burden with a reduction of at least 2 units of RBCs (hematological improvement) for any 12-week rolling time period – Day 2 to 85, Day 3 to 86, etc. through Day 170 to Day 253 (Week 36) – compared to the 12 weeks prior to Baseline (Day 1).	X	
Proportion of subjects with a $\geq 20\%$ reduction in RBC transfusion burden with a reduction of at least 2 units of RBCs (hematological improvement) for any 14-week rolling time period – Day 2 to 99, Day 3 to 100, etc. through Day 156 to Day 253 (Week 36) – compared to the 12 weeks prior to Baseline (Day 1).	X	
Proportion of subjects with a $\geq 33\%$ reduction in RBC transfusion burden with a reduction of at least 2 units of RBCs (hematological improvement) for Week 12 to Week 24 and Week 24 to Week 36, compared to the 12 weeks prior to Baseline (Day 1).	X	
Proportion of subjects with a $\geq 33\%$ reduction in RBC transfusion burden with a reduction of at least 2 units of RBCs (hematological improvement) for Week 12 to Week 36, compared to the 12 weeks prior to Baseline (Day 1).	X	

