13.6.2.5 Physical Examinations

All physical examination findings will be listed in by-subject listings on the Safety Analysis Set. No tabulation summaries will be provided.

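### Coagulation is in the primary safety endpoint but has no planned by-arm change summary, physical examination is listing-only, and maximum-only shift plots hide a transient fall in neutrophils or platelets

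*SAP*

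**What the plan says.** SAP 9.0 lists among the primary endpoints "Changes from Baseline in 12-lead ECG clinical laboratory test (chemistry, hematology, coagulation, and urinalysis), and vital signs parameters (continuous parameters only"), and separately "Changes in physical examination findings relative to the Baseline physical examination". SAP 13.6.2 repeats both; its laboratory item begins "Changes from Baseline in clinical laboratory tests (hematology, coagulation chemistry, urinalysis"). SAP 10.1.10 defines analysis visit windows for coagulation in both populations (Weeks 12, 24 and 36).

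The outputs are specified in SAP 13.6.2.2:

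- Panels to be summarized: "Clinical laboratory tests (serum chemistry, central laboratory hematology, local laboratory hematology, and specialty hematology) will be summarized using the Safety Analysis Set".
- Observed values and changes from Baseline, by visit and arm, are "presented separately for chemistry and hematology and for each population".
- CTCAE shift tables by arm draw on Appendix 4, but the sentence restricts them to selected hematology and chemistry parameters.
- The figure list has coagulation in its heading but names no PT, aPTT or INR. For each named parameter, including neutrophils and platelets, it plans a "Shift plot from baseline to post-baseline maximum value for each parameter by treatment arm and for the combined IMR-687 treatment arms" and a box plot by visit.
- Listings: "All laboratory parameters (serum chemistry, central laboratory hematology, local laboratory hematology, specialty hematology, coagulation, and urinalysis) will be displayed in individual subject data listings".

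For physical examination, SAP 13.6.2.5 plans by-subject listings and adds "No tabulation summaries will be provided".

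**The concern.** The primary objective is safety, so each named component of the primary endpoint should lead to an output that lets IMR-687 be set beside placebo. Vital signs and ECG have by-arm change tables (13.6.2.3 and 13.6.2.4), as do chemistry and hematology. Coagulation and physical examination do not. A programmer who followed 13.6.2.2 and 13.6.2.5 exactly would deliver no by-arm summary of change from Baseline for either. A reader of the study report would have to build that comparison from listings.

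The shift plots raise a different issue. Protocol 5.2 anticipates a profile without myelosuppression, and inclusion criterion 9 admits subjects on stable hydroxyurea, so a fall in neutrophils or platelets is a relevant signal. A plot of baseline against the highest later value is poorly suited to showing it.

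**Working it through.** There is no stated figure to reproduce. The check traces each component to its outputs and then asks what a maximum-only plot can show.

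**1. Component against by-arm output**

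| Item | By-visit change table by arm | CTCAE shift table by arm | Figure by arm | Listing |
|---|---|---|---|---|
| PT | not planned | not graded in Appendix 4 | not named | yes |
| aPTT | not planned | graded in Appendix 4, outside the wording of 13.6.2.2 | not named | yes |
| INR | not planned | graded in Appendix 4, outside the wording of 13.6.2.2 | not named | yes |
| Physical examination | not planned | not applicable | none | yes |
| Neutrophils, platelets | planned | planned, decreases graded | maximum shift plot and by-visit box plot | yes |

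The pharmacodynamic analyses do not fill the gap. Protocol 11.3.6.2 says some coagulation tests are also PD endpoints, but SAP 13.6.8 lists none. SAP 6.1 does not declare either omission as a change from the protocol.

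**2. Number of post-baseline counts**

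These come from the hematology rows of the schedules of assessments.

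- TDT: Weeks 1, 3, 6, 12, 18, 24, 30, 36 and 40, so k = 9.
- NTDT: Weeks 1, 4, 8, 12, 16, 20, 24, 28, 32, 36 and 40, so k = 11.

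**3. Maximum against baseline with no drug effect**

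SAP 10.1.2 uses a single Baseline value for these safety tests. Assume that value and the k later values are exchangeable. Baseline is then equally likely to hold any of the k + 1 ranks, and the later maximum exceeds it unless baseline is the largest:

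P(maximum > baseline) = k/(k + 1)

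- TDT: 9/10 = 90%
- NTDT: 11/12 = 91.7%, about 92%

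**4. The same proportion when counts do fall**

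This is a simulation of 400,000 subjects per population. It assumes independent normal values with equal within-subject SD.

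| Scenario | TDT | NTDT |
|---|---|---|
| Fall of 5 SD at one visit only | 89% | 91% |
| Fall of 1 SD at every visit | 66% | 69% |
| Fall of 2 SD at every visit | 33% | 36% |
| Fall of 3 SD at every visit | 10% | 11% |

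A deep fall at one visit moves the proportion by about one percentage point. A large fall held at every visit does show, because most maxima then lie below baseline.

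**5. Example**

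A subject whose neutrophils go from 4.0 to 0.9 x 10^9/L at one visit and then recover can plot in the same place as one whose count never fell. The CTCAE shift table would record that value as Grade 3, since Appendix 4 sets Grade 3 at below 1.0 down to 0.5 x 10^9/L.

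**The case against.** **Coagulation.** A reader might infer that it has no by-arm output at all. The documents do not establish that. Section 13.6.2.2 is the only place that uses Appendix 4, and Appendix 4 grades aPTT and INR; the INR row even carries a rule for identifying anticoagulant use. Coagulation has its own analysis windows. Where listing-only output is intended for a laboratory test, as with character urinalysis, the SAP says so. Protocol 13.3 promises summaries of clinical laboratory variables, and under Protocol 11.3.6 clinically significant results after screening are recorded as adverse events. The shift-table sentence may therefore be loose drafting. What stands is that inclusion of aPTT and INR is ambiguous, PT is missing on any reading, and a grade shift is not the change from Baseline that the endpoint names.

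**Physical examination.** A reader might infer that examination findings cannot be compared between arms. That goes too far. Under Protocol 11.3.4, clinically significant new or worsened findings that meet the adverse event definition go on the adverse event form, and SAP 13.6.2.1 tabulates adverse events by arm. Listing-only output is an open choice, Protocol 13.3 does not name examination among its data summaries, and complete examinations after Baseline occur only at Weeks 24 and 36. What stands is that the endpoint is worded as change from Baseline and no output reports that.

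**Shift plots.** A reader might infer that the plots cannot show any fall, or that the plan conceals falling counts. Neither is supported. A large sustained fall would show in the plots. By-visit change tables, by-visit box plots and CTCAE shift tables all show decreases, and the shift tables include unscheduled visits. The upward tilt of the maximum applies to every arm, placebo included, so it does not by itself favour one. For platelets the documents also care about the high side: exclusion criterion 9 and the only platelet criterion in SAP Table 5 are both set above 1000 x 10^9/L. One limit remains. When several results fall in one window, by-visit outputs keep the one closest to the scheduled day (SAP 10.1.10), so an off-schedule low value can drop out and leave the graded shift table as the only by-arm output that shows it.

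**Conclusion.** The concern holds in limited form. Coagulation has three tests (PT, aPTT, INR), none with a planned by-arm change summary or named figure. Two are ambiguous for the CTCAE shift tables and one is absent from them. This is a mismatch between the stated primary endpoint and its analysis, and looks like an oversight. The physical examination gap is real but secondary, because it is an explicit choice with partial cover through adverse events.

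The shift-plot weakness is confined to transient falls and to that one display. The 90% and 92% figures rest on exchangeability, and the simulated figures on independent normal values with equal SD; they illustrate how the plot behaves and do not predict this trial's data. Nothing here shows that the safety conclusions would be biased. The corrections are nevertheless worth making because they are cheap and specific.

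**What to change.** In SAP 13.6.2.2:

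- Add PT, aPTT and INR to the by-visit tables of observed values and changes from Baseline, by arm.
- Extend the shift-table sentence to coagulation parameters in Appendix 4, so that aPTT and INR are clearly included.
- Plot neutrophils as baseline against post-baseline minimum, and platelets against both minimum and maximum.

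As a second priority, do one of two things for physical examination. Either tabulate by arm, in 13.6.2.5, the subjects with a new or worsened abnormality at Weeks 24 and 36, or state in 9.0 and 13.6.2 that examination changes are assessed through listings and adverse events.

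Cost: a few extra tables and a changed plotting variable. All the data are already collected.
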